1.2 Trial Rationale

1.2.1 Justification for patient population

Despite the approval of a number of aTNF α therapies, vedolizumab and ustekinumab in CD, there is still a significant unmet need for effective therapies for the induction of clinical and endoscopic remission in moderate to severely active CD. The addition of a new biologic with a different mechanism of action will allow greater flexibility in treatment regimens and potentially combination therapy. An anti-IL-18 antibody is hypothesised to benefit patients with CD by a number of mechanisms including reduction of IL-18 drive to T cell differentiation and proliferation and inhibition of IFN- γ production.

The purpose of this trial is to investigate the safety and tolerability of GSK1070806 administered intravenously once on Day 1 for the treatment of patients with moderate to severely active CD as defined by CDAI and confirmed by endoscopy. Clinical activity will be measured using the CDAI, Patient Reported Outcome (PRO) of diarrhoea and abdominal pain, and by direct assessment of inflammation in the colon and terminal ileum using endoscopy and Simple Endoscopic Score for CD (SES-CD). Changes in faecal biomarkers of disease and biomarkers of systemic inflammatory status shall also be assessed.

One of the further key aims of this trial is to gain a better understanding of the molecular pathways through which GSK1070806 achieves a therapeutic benefit in CD. To enable this assessment, gut mucosal biopsies shall be taken pre-dose and at 12-weeks post-dose and will be evaluated/analysed by staff at the University of Birmingham (UoB) Institute of Translational Medicine (ITM) stratified medicine laboratory and GlaxoSmithKline(GSK).

1.2.2 Justification for design

The proposed trial will be a randomised, double-blind, placebo-controlled, trial to investigate the safety, tolerability, pharmacokinetics, pharmacodynamics and clinical activity of single intravenous infusion of GSK1070806 in patients with moderate-to-severe active CD.

A placebo controlled design is chosen as the most sensitive for determining effect size and benefit: risk profile of GSK1070806. Since subjects are allowed to continue with certain protocol-defined CD maintenance medications in stable doses, many will, in fact, be receiving some treatment over and above placebo making this more acceptable to both physicians and patients.

1.2.3 Choice of treatment

Single induction dosing of GSK1070806 given intravenously at a dose of 10 mg/kg is proposed for the trial.

A wide range of doses of GSK1070806 were investigated in the clinic so far;

- Single dose of GSK1070806 from 0.008 mg/kg up to 10 mg/kg in healthy volunteers and from 0.25 mg/kg to 3 mg/kg in obese participants;
- Two repeat doses of either 0.25 or 5 mg/kg 28 days apart in patients with type2 diabetes
- Single dose of 3 mg/kg in the renal transplant study.

These doses have been well tolerated with an acceptable safety profile.

As targeting IL-18 in CD patients is an unprecedented mechanism, a dose of 10 mg/kg has been selected to fully test the mechanism of action. This dose is predicted to maximise pharmacological and clinical effects, based on the ex-vivo pharmacodynamics effects that were observed in the whole blood stimulation assay during the first treatment in human (FTIH) trial in healthy and obese participants (NCT01035645), while also taking into account the change in the population studied. Maximum effect was observed up to day 56 in particular on IFN- γ with no clear differentiation between 1 and 3 mg/kg in healthy volunteers. Suppression of IL-18 in plasma was achieved at significantly lower doses, with 99.9% occupancy sustained for 90 days at a dose of 0.3mg/kg in the FTIH study. Simulations using a physiologically based pharmacokinetic model based on the two pore hypothesis predict that a dose of 10 mg/kg is required to maintain >99% IL-18 suppression in the gut interstitium for 90 days, while >90% suppression can be achieved with a dose of 1 mg/kg.

2. OBJECTIVES AND OUTCOME MEASURES

2.1 Primary Objective

To evaluate the safety and tolerability of single dose intravenous (IV) administrations of GSK1070806 in patients with moderate to severe Crohn's disease.

2.2 Primary Outcome Measure

Safety and tolerability parameters include: adverse events, serious adverse, clinical laboratory tests, electrocardiograms, and vital signs. Frequency, type and severity of infections.

2.3 Secondary Objectives

- 1. To evaluate the clinical activity of single dose IV administrations of GSK1070806 in patients with moderate to severe CD.
- 2. To evaluate the serum pharmacokinetics (PK) following single dose IV administrations of GSK1070806 in patients with moderate to severe CD.
- 3. To evaluate the proportion of patients with moderate to severe Crohn's disease achieving clinical remission following single dose IV administrations of GSK1070806.
- 4. Time to clinical response following single dose IV administrations of GSK1070806 in patients with moderate to severe CD.
- 5. To evaluate the effect of GSK1070806 on established biomarkers of disease in patients with moderate to severe Crohn's disease.
- 6. To evaluate the potential of anti-GSK1070806 antibody formation following administration of GSK1070806 in patients with moderate to severe CD.

2.4 Key Secondary Outcome Measure

CDAI score over time (refer to Schedule of Events for assessment times).

2.5 Further Secondary Outcome Measures (Non-Hierarchical)

- 1. Serum concentrations of GSK1070806 over time and derived PK parameters if feasible AUC(0- τ), Cmax, Tmax and t½.
- 2. Abdominal pain (AP) over time (refer to Schedule of Events for assessment times).
- 3. Stool frequency (SF) over time (refer to Schedule of Events for assessment times).
- 4. Post-treatment (w12) SES-CD endoscopic score.
- 5. Proportion of patients in clinical remission defined as average daily Stool Frequency \leq 2.8 and /or average daily Abdominal pain \leq 1 and CDAI <150.

- Kinetics of induction of clinical response defined as a ≥ 70 point decrease from baseline CDAI score (or score ≤ 150).
- 7. Serum C-reactive protein over time (refer to Schedule of Events for assessment times).
- 8. Faecal calprotectin over time (refer to Schedule of Events for assessment times).
- 9. Incidence and titers of serum of anti-GSK1070806 antibodies before and after GSK1070806 administration.

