01	13-Mar-2019	5.0	Substantial Amendment	 Schedule of Events – Information regarding endoscopy images added. Information Clarification on when Patient Daily Diary should be completed Additional information included regarding photographic images and/or video recordings in Sections 3, 5 and 7 Update of Section 6.2 Emergency Randomisation Minor typos throughout
02	12-Aug-2019	6.0	Substantial Amendment	 Reduction in sample size from 30 to 21 Removal of CDAI score from Eligibility Criteria Clarification of PK and PD sampling. EOI and 4-8hour sample for Visit 3 PD removed. Visit 9 PK removed. Clarification of screening endoscopy timepoint and biopsy samples Change to permitted concomitant medications (washout) and prohibited medications Change of SAE reporting email address Amendment to CRFs. Removal of SES-CD CRF. Inclusion of Endoscopy Score Form CRF Removal of 2nd interim analysis

TRIAL SYNOPSIS

Trial Title	A Phase Ib/IIa, Randomised, Double Blind, Placebo-Controlled Trial to Investigate the Safety, Tolerability and Clinical Activity of Humanised Antibody GSK1070806 in the Treatment of Patients with Moderate-to-Severe Crohn's Disease
Trial Design	A randomised, double-blind, placebo-controlled trial in patients with moderate-to- severe active Crohn's disease
Trial Duration	3 years (12-18 months recruitment period)
Patient Population	Adult patients with Crohn's disease
Sample Size	21

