Objectives	 Primary Objective To evaluate the safety and tolerability of single dose intravenous (IV) administrations of GSK1070806 in patients with moderate to severe Crohn's disease. Secondary Objectives 1. To evaluate the clinical activity of single dose IV administrations of GSK1070806 in patients with moderate to severe Crohn's disease. 2. To evaluate the serum pharmacokinetics (PK) following single dose IV administrations of GSK1070806 in patients with moderate to severe Crohn's disease. 3. To evaluate the proportion of patients with moderate to severe Crohn's disease. 3. To evaluate the proportion of patients with moderate to severe Crohn's disease achieving clinical remission following single dose IV administrations of GSK1070806. 4. Time to clinical response following single dose IV administrations of GSK1070806 in patients with moderate to severe Crohn's disease. 5. To evaluate the effect of GSK1070806 on established biomarkers of disease in patients with moderate to severe Crohn's disease. 6. To evaluate the potential of anti-GSK1070806 antibody formation following administration of GSK1070806 in patients with moderate to severe Crohn's disease.
Outcome Measures	Primary Outcome Measures Safety and tolerability parameters include: adverse events, serious adverse events, clinical laboratory tests, electrocardiograms and vital signs. Frequency, type and severity of infections. Key Secondary Outcome Measure CDAI score over time (refer to Schedule of Events for assessment times).

	Further Secondary Outcome Measures
	 Serum concentrations of GSK1070806 over time and derived PK parameters if feasible AUC(0-τ). Cmax. Tmax and t%.
	 Abdominal pain (AP) over time (refer to Schedule of Events for assessment times)
	3. Stool frequency (SF) over time (refer to Schedule of Events for assessment times)
	4. Post-treatment (w12) SES-CD endoscopic score.
	 Proportion of patients in clinical remission defined as average daily Stool Frequency < 2.8 and /or average daily Abdominal pain < 1 and CDAI <150.
	 Kinetics of induction of clinical response defined as a ≥ 70 point decrease from baseline CDAI score (or score ≤ 150).
	 Serum C-reactive protein over time (refer to Schedule of Events for assessment times).
	8. Faecal calprotectin over time (refer to Schedule of Events for assessment times).
	 Incidence and titers of serum of anti-GSK1070806 antibodies before and after GSK1070806 administration
Main Inclusion and	Inclusion Criteria

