4. ELIGIBILITY

4.1 Inclusion Criteria

A patient will be eligible for inclusion in this study only if all of the following criteria apply:

- 1. Written informed consent prior to any of the screening procedures including discontinuation of prohibited medications. (see Section 7.11 for additional information)
- 2. Patients must have been diagnosed with Crohn's disease at least 3 months prior to Screening Visit 1
- 3. Patients are required to have endoscopic evidence of active Crohn's disease at Baseline defined by endoscopic appearance: SES-CD excluding the narrowed component of \geq 6 (or \geq 4 for patients with isolated ileal disease).
- 4. AST and ALT \leq 2xULN; alkaline phosphatase and bilirubin \leq 1.5xULN (isolated bilirubin >1.5xULN is acceptable if bilirubin is fractionated and direct bilirubin <35%)
- 5. Male or female participants aged \geq 16 years (up to 80 years)

Male participants:

6. A male participant must agree to use contraception as detailed in Appendix 5 of this protocol for at least 180 days post-dose of study medication and refrain from donating sperm during this period.

Female participants:

- 7. If the patient is breastfeeding, she must agree to stop breastfeeding once randomised into the trial. ¹
- 8. A patient is eligible to participate if she is not pregnant.
- 9. A woman of childbearing potential (WOCBP) is eligible only if she meets at least one of the following conditions:
 - Females on HRT and whose menopausal status is in doubt will be required to use one of the non-hormonal highly effective contraception methods if they wish to continue their HRT during the trial. Otherwise, they must discontinue HRT to allow confirmation of postmenopausal status before trial enrolment.
 - Agrees to follow the contraceptive guidance in Appendix 5 for at least 180 days post-dose of trial medication. If a hormonal method of birth control is selected from the list in Appendix 5 then patients must have been using these methods at least 1 month prior to GSK1070806 administration, or be abstinent, or utilise a condom as a method of contraception until the selected hormonal method has been in place for the 28 day period.
- 10. A woman who is not of childbearing potential is eligible only if she meets at least one of the following conditions:
 - i. Premenopausal female with documented hysterectomy
 - ii Premenopausal female with documented bilateral salpingectomy or oophorectomy

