12.3.1 Simulating CDAI paths for patients in a scenario

- 1) Baseline values of CDAI score for patients allocated to placebo and GSK1070806 are randomly sampled from a Normal (285, 80²) distribution. Thus, baseline CDAI scores are centred at 285 and 95% of values are in the approximate interval (125, 445).
- 2) Vectors of treatment-effects at weeks (0, 2, 4, 8, 12, 16, 24) are selected for placebo, $\lambda_P(t)$, and GSK1070806, $\lambda_E(t)$. These reflect the value of the mean CDAI path through time as a multiple of the baseline value. Values less then 1 show improvement, i.e. falling CDAI scores. The chosen subscripts are *P* for placebo and *E* for experimental treatment.
- 3) The value at time t of the CDAI path for a patient with baseline score y_0 allocated to treatment A is

$$y_0 * \lambda_A(t) + \epsilon$$

where ε is a noise term, distributed N(0, 30²). For instance, if a patient has y₀ = 300, is allocated to GSK1070806 with $\lambda_{E}(t) = 0.9$, and happens to take $\varepsilon = 12$ at time *t*, then for that patient:

CDAID

The mean baseline value and variability of baseline scores were selected to mimic those reported in a recentlypublished randomised controlled trial (RCT) of CD: (Zhang, Lv et al. 2018). Under the described method, the variability of CDAI scores are driven by the variability of the baseline scores and the noise terms. The variance of the noise, 302, was chosen by trial-and-error so that the overall variability of the CDAI scores approximately matched those at the time horizons reported in [Zhang et al. 2017].

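### With no CDAI floor at entry, the score-of-150-or-below limb counts a patient who starts there as a responder without any change, and the remission rule lacks brackets

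*Protocol*

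**What the plan says.** Response is defined in Section 2.5, and in the same terms in the synopsis: "Kinetics of induction of clinical response defined as a ≥ 70 point decrease from baseline CDAI score (or score ≤ 150". The two limbs are alternatives, and the second does not refer to the baseline score.

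Remission is given in the synopsis as "average daily Stool Frequency < 2.8 and /or average daily Abdominal pain < 1 and CDAI <150". Section 2.5 has the same structure and also has no brackets. The inequality signs for stool frequency (SF) and abdominal pain (AP) look different in the two places. That may come from text extraction, and nothing here depends on it.

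For entry, Section 4.1 states: "Patients are required to have endoscopic evidence of active Crohn's disease at Baseline defined by endoscopic appearance". The criterion is an SES-CD threshold. No inclusion criterion in 4.1 and no exclusion criterion in 4.2 sets a minimum CDAI. The amendment log explains why: "Removal of CDAI score from Eligibility Criteria". Section 1.2.1 nevertheless still describes the population as "moderate to severely active CD as defined by CDAI and confirmed by endoscopy".

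The only documented baseline distribution is in Section 12.3.1: "baseline CDAI scores are centred at 285 and 95% of values are in the approximate interval (125, 445".

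Remission and time to response are secondary objectives 3 and 4 (Section 2.3). Section 12.2.2 sends dichotomous outcomes such as response to Fisher's exact test by arm.

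**The concern.** An absolute threshold can stand in for improvement only if patients start above it. For anyone entering at 220 or more the second limb adds nothing, because reaching 150 from 220 is already a fall of 70. For a patient entering between 150 and 220 it credits a smaller fall that crosses the threshold, which is a defensible choice. For a patient entering at or below 150 it credits no fall at all: someone who starts at 140 and stays at 140 is a responder at the first visit.

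That patient is also an immediate event in time to response. Being below 150, the same patient satisfies the CDAI part of remission from the start, so remission is not something achieved after dosing. Fisher's exact test makes no adjustment for baseline. With 7 patients on placebo (21 randomised 2:1), one such patient moves that arm's rate by 1/7, or 14 percentage points.

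The remission rule has a separate problem. Without brackets it can be read in at least three ways, and the choice would otherwise be open when the data are seen.

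**Working it through.** **Inputs.** Section 12.3.1: baseline Normal(285, 80²); later score = baseline × λ(t) + noise, noise SD 30. Table 10: λ at weeks 2 to 24. Section 3.1: 21 patients, 2:1, so 14 and 7.

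**The plan's own figure.** 285 ± 2 × 80 = (125, 445), as stated. A score of 125 therefore lies inside the model's central 95%, although it is below the response threshold.

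**How many start at or below 150.**
- Φ((150 − 285)/80) = Φ(−1.69) = 0.046; expected number 21 × 0.0458 = 0.96.
- At least one of 21: 1 − (1 − 0.0458)^21 = 63%. At least two: 25%.
- At least one of 7 on placebo: 1 − (1 − 0.0458)^7 = 28%. At least two: 3.8%.

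The distribution without a CDAI floor is not documented. Assumed alternatives:

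| Baseline (assumption) | Share at or below 150 | Expected of 21 |
|---|---|---|
| Normal(285, 60²) | 1.2% | 0.3 |
| Normal(285, 100²) | 8.9% | 1.9 |
| Normal(250, 80²) | 10.6% | 2.2 |
| Normal(220, 80²) | 19.1% | 4.0 |

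**Response with no drug effect (Table 10 column A, Normal(285, 80²), simulated).**
- Of patients starting at or below 150, about 80% are responders at week 2, 80.5% at week 12, and 99.9% at one or more of the modelled visits. Only 1.2% have a 70-point fall at week 12.
- Week-12 response over all patients is 7.4% as written. Patients starting at or below 150 contribute 4.58% × 80.5% = 3.7 points, about half.
- If the 150 limb requires baseline above 150, the loss is 4.58% × (80.5% − 1.2%) = 3.6 points, leaving 3.8%. The 70-point fall alone gives 1.6%.

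**Effect on the contrast between arms.** Week-12 response, drug minus placebo, in percentage points (simulated, same baseline; accurate to about 0.1):

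| Scenario | As written | Limb limited to baseline >150, all patients kept | 70-point fall alone | Only patients with baseline >150 |
|---|---|---|---|---|
| 2 | 43.7 | 43.3 | 40.1 | 45.0 |
| 3 | 26.9 | 26.6 | 24.0 | 27.6 |
| 4 | 33.5 | 33.1 | 30.3 | 34.4 |
| 5 | 46.8 | 47.0 | 45.7 | 48.7 |

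The last column removes the low-baseline patients from numerator and denominator. For scenario 2:
- drug: (0.510 − 0.0458 × 0.950)/0.954 = 0.489;
- placebo: (0.0742 − 0.0458 × 0.805)/0.954 = 0.039;
- difference: 45.0 points.

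The dilution is thus 0.7 to 1.9 points. At an assumed mean of 220, scenario 2 goes from 33.0 to about 38.0, a dilution of about 5 points.

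**Remission readings.** Take (i) SF and AP and CDAI; (ii) (SF or AP) and CDAI; (iii) SF or (AP and CDAI). They disagree on 4 of the 8 possible patterns:

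| SF met | AP met | CDAI met | (i) | (ii) | (iii) |
|---|---|---|---|---|---|
| no | yes | yes | no | yes | yes |
| yes | no | yes | no | yes | yes |
| yes | no | no | no | no | yes |
| yes | yes | no | no | no | yes |

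Under (iii) a patient with CDAI of 150 or more can be in remission.

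**The case against.** The strongest reply is about scale, and most of it stands. Section 12 defines success on the mean CDAI profile and gives the other secondary measures a supportive role; Section 2.5 calls them non-hierarchical. The expected number of patients concerned is about one, and the chance of none is 37%. The larger shares at means of 250 and 220 are assumptions.

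A reader might infer that these automatic responders pull the comparison to zero, or that one or two of them decide it. The documents do not support either. In the protocol's active scenarios the 150 limb leaves the week-12 contrast about the same or larger than a 70-point fall alone. Two or more low-baseline patients in the placebo arm have a probability of only 3.8%. The same figures show why a 70-point fall alone is not the natural first repair: it shrinks the contrast in all four active scenarios.

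Nor should the share of patients who ever respond with no drug effect over weeks 2 to 24, about 19.5%, be put down to this defect. Patients already at or below 150 make up about 23% of those responders, and with the limb restricted the figure is still about 15.3%. Much of it is noise over repeated visits.

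On remission, a reader might infer that all three criteria are required. The conjunction used supports that reading least. Section 3.1 names SF and/or AP together and CDAI separately, which favours (SF or AP) and CDAI below 150.

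It can also be said that low-baseline patients are a derivation rule for the SAP, and that Section 12.4 makes every dosed patient evaluable. But the protocol itself states both definitions. An SAP that added a baseline condition or chose a bracketing would be altering a stated outcome, so the change belongs in the protocol.

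**Conclusion.** The response rule is wrong as written: in a trial with no CDAI floor it counts absence of change as response. Under Normal(285, 80²) this concerns about 1 patient of 21 (63% chance of at least one). It accounts for about half of an apparent week-12 response rate of 7.4% under no drug effect.

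The damage is to absolute response rates and, most directly, to time to response, where such patients become early events without improving. Patients entering below 150 have the same head start on remission. The dilution of the week-12 contrast is small, about 1 to 2 points at mean 285, and larger only if the true mean is well below that. Safety and the CDAI model are untouched.

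The sizes rest on the protocol's simulation model. Its baseline was set to mimic a published trial, and the documents do not show that it describes patients enrolled without a CDAI criterion. The remission rule is ambiguous on its face, whatever the baseline distribution. The Section 1.2.1 mismatch is editorial. Overall this is a modest correction to supportive outcomes, worth making before unblinding.

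**What to change.** 1. In Section 2.5 and the synopsis, let a score of 150 or below count as response only for patients whose baseline CDAI is above 150.
2. Compute response, time to response and remission among patients with baseline CDAI above 150, and list the remaining patients separately by arm. State that this set applies to these three outcomes only, so that it sits alongside Section 12.4.
3. Write the remission rule with explicit brackets. Section 3.1 supports (SF or AP) and CDAI below 150; the sponsor should confirm the intended reading before unblinding.
4. Reconcile the description of the population in Section 1.2.1 with Section 4.1.

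The cost is a few lines of wording. Baseline CDAI is measured before dosing and already collected, so restricting on it does not condition on treatment. About one patient is expected to leave these denominators (up to about four if the mean were 220); all stay in the CDAI model and the safety analysis.

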2.6 Exploratory Objectives (Non-Hierarchical)

- 1. To evaluate the pharmacodynamics (PD) effects of GSK1070806 in participants with Crohn's disease.
- 2. To evaluate the proportion of patients with Crohn's disease achieving endoscopic response following single dose IV administration of GSK1070806 at week 12.
- 3. To identify genetic variations associated with drug response and disease activity in Crohn's and related diseases.

